Several studies have assessed the prevalence of overactive bladder among different population age groups, ethnicities, or genders with varying results. It was rated to be 11.8% in a multicenter cross-sectional study including several countries in Canada and Europe (Germany, Italy, Sweden, and the UK (Irwin et al., 2006), while in the USA it was estimated to be 16% (Stewart et al., 2003). All these studies were conducted on the general population; however, in China, it was about 6% among university students (Liang et al., 2022).

In the Arab world, several cross-sectional studies have also assessed the prevalence of overactive bladder, including students, and its effect on the quality of life. Hajjar 2022 (Hajjar et al., 2022) assessed its prevalence among Lebanese female nulliparae university students. They showed that nocturia and frequency were the most common symptoms that bothered students. They also found a statistical correlation between smoking, drinking coffee, or tea, and increased symptoms. Also, drinking soft drinks was associated with an increase in urinary leakage. Additionally, Abuorouq 2024(Abuorouq et al., 2024) and Shawahna 2021(Shawahna et al., 2021)

Cross-sectional studies were conducted on medical students in Jordan and Palestine, respectively. They reported a prevalence of 44.5% and 54.1%, respectively. Shawahna 2021(Shawahna et al., 2021) reported a statistically significant correlation between gender or stressful life and a decrease in quality of life.

Rational

In Egypt, the prevalence of overactive bladder is underestimated. A single previous multinational cross-sectional study across several Arab countries, including Egypt, was conducted. (Al Edwan et al., 2021) was conducted in Egypt, Algeria, Jordan, and Lebanon among women. They reported a prevalence of 57.5% among Egyptian women.

Since this study, no study has been conducted to further assess its prevalence in different age or gender groups in Egypt. Taking into consideration the stressful life of medical students in Egypt, and several life risk factors they face, we will conduct this cross-sectional study.

No previous cross-sectional study was conducted on the medical students in Egypt before.

We aim to assess the prevalence of overactive bladder among Egyptian medical students. We will also assess the risk factors associated with an increase in this condition and its effect on their quality of life.

Research Questions

What is the prevalence of the overactive bladder among Egyptian medical students, how can this affect their quality of life, and what are the risk factors that can increase its prevalence?

Hypothesis

We hypothesize that overactive bladder is a common condition in Egyptian medical students.

Aim:

Improve the quality of life of medical students by addressing the prevalence of overactive bladder and its risk factors

Objective

- To assess the prevalence of overactive bladder among Egyptian medical students.
- To assess its effect on their quality of life
- To address the risk factors that can increase the prevalence of this condition.

Methodology

A. Technical design

- **Study design:** Analytical cross-sectional study
- **Study sitting:** a medical student in Egypt will be accessed through an online questionnaire.
- **Study population:** Egyptian Medical students studying medicine in Egypt.
- **Time:** 2025-2026
- **Inclusion criteria**
 - Medical student studying human medicine in Egypt
 - Their age ranges from 18 to 27 years old
 - Egyptian person
- **Exclusion criteria**
 - Incomplete data
 - Wrong data in the questionnaire
 - Students refuse to participate

- **Sampling**

We calculated the sample size based on the total medical students in Egypt, which is 121,320, according to the Central Agency for Public Mobilization and Statistics (CAPMAS) 2023-2024(*Capmas*, n.d.). The expected prevalence of overactive bladder is 50%(Abuorouq et al., 2024; Shawahna et al., 2021). Using the total sample size, expected prevalence rate, an 80% power, 95% confidence interval (95% CI), and a 5% error margin, we calculated the sample size via Epi Info version 7.2.60(*Epi InfoTM | CDC*, n.d.) to become 384, and adding a 10% non-response rate, the final sample size will be 422 students

- **Sampling techniques:** The convenient sampling will be applied in this study

B. Operational design

- **Pilot study:** We will perform a pilot study to assess the readability of the questionnaire. We will perform it on 40 students, and any changes in the questionnaire will be made. Pilot study data will be excluded from the data analysis
- **Study field:** an online questionnaire will be shared through social media platforms such as WhatsApp, Facebook, or Telegram.

Data collection method

Students are required to fill out the online questionnaire. It is divided into three main categories.

1. Sociodemographic data in which we ask about students' age, sex, and academic year. We also ask about their life risk factors, such as body weight, presence of chronic disease, previous surgery, stressful life, and soft drinks(Abuorouq et al., 2024).
2. Questions about the presence of overactive bladder symptoms.(Coyne et al., 2015) The questions are taken from the 6-item ask about the presence of overactive bladder symptoms in the past 4 weeks

This scale consists of 6 items, and each one has 6 available answers that range from not at all, which indicates the absence of the symptoms, to a very great deal, which indicates the presence of these symptoms. The score of each question ranges from 1 to 6, and the total score is 36. A score of 18 or more indicates the presence of the overactive bladder symptoms

3. Part 3 asks about the quality of life affected by the overactive bladder. This part is taken from the quality of life questionnaire part of the Overactive Bladder Symptom and Health-Related Quality of Life Short-Form (OAB-q SF)(Coyne et al., 2015). This is a 13-item questionnaire, each one has 6 answers (None of the time, a little of the time, some of the time, A good bite of the time, Most of the time, All of the time). Each question scores from 1 to 6, so the total score ranges from 13 to 78

- **Statistical analysis**

We will summarize the data first according to its type. Categorical data will be summarized into numbers and percentages, while continuous data will be assessed for normality first; if it is normally distributed, we will use mean and standard deviation (SD), and if not, median and interquartile range will be used (IQR).

Differential statistics will be conducted via the Mann-Whitney U test. We will assess the difference between the baseline data, such as sex, academic year, on the overactive bladder prevalence and its effect on quality of life.

Also, we intended to perform a logistic regression to assess the relation between overactive bladder symptoms and quality of life, and the relation between risk factors, such as history of UTI, soft drinks, coffee, or tea, on the presence of overactive bladder symptoms.

All statistics will be conducted using SPSS version 29.

C. Administrative design

- **Ethical considerations**

- The study protocol will be approved by the Institutional Review Board of Zagazig University, Faculty of Medicine
- Study participants will be included after informed consent.

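### Objective 3 and the research question use causal wording that one cross-sectional questionnaire cannot support; the protocol describes no timing or habit-change item for drinks

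*Protocol*

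**What the plan says.** The Objective list in the Protocol includes "To address the risk factors that can increase the prevalence of this condition", and the Research Questions section asks "what are the risk factors that can increase its prevalence". The Rational section is softer: "We will also assess the risk factors associated with an increase in this condition and its effect on their quality of life".

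Technical design names the study an "Analytical cross-sectional study". Under Data collection method, one form holds both exposures and outcome: "Students are required to fill out the online questionnaire. It is divided into three main categories". Part 1 covers risk factors, "such as body weight, presence of chronic disease, previous surgery, stressful life, and soft drinks". Part 2 is the six-item symptom scale over the past 4 weeks, with 18 or more counted as overactive bladder.

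Statistical analysis plans a logistic regression of "the relation between risk factors, such as history of UTI, soft drinks, coffee, or tea, on the presence of overactive bladder symptoms". Coffee, tea and history of UTI appear there but not among the part 1 examples. Stress appears among the part 1 examples but not among the regression examples.

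**The concern.** The objective and research question ask what raises prevalence, whereas the data will show only what accompanies symptoms at one moment. The gap matters most for drinks, because intake is something a person can change in response to symptoms. A student troubled by frequency who gives up coffee, tea or soft drinks is a case who may be recorded as a low consumer. The outcome has a stated window and the drink exposures have none. The protocol also describes no symptom-onset item and no question on habit change, so the analysis could not detect this pattern.

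If enough symptomatic students have cut down, a drink that raises risk could appear unrelated to symptoms, or even protective. Stress could be distorted the opposite way, because symptoms may themselves raise reported stress. The stated Aim is to improve students' quality of life by addressing prevalence and risk factors, so a misread direction would feed into that Aim.

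**Working it through.** **The plan's own figures.** The protocol gives no figure on this point. Its sample size supplies only the scale. With p = 0.5, d = 0.05 and z = 1.96, z²p(1−p)/d² = 384, and 384 × 1.10 = 422. Both stated values reproduce.

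**Inputs.** Prevalence of 50% is from the Sampling paragraph. The true odds ratio (OR), the share of students who drink (e) and the share of symptomatic drinkers who have stopped (f) are assumptions, because the documents give none.

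**Set-up.** Let p1 and p0 be the prevalence in drinkers and non-drinkers, with odds(p1) = OR × odds(p0) and e·p1 + (1−e)·p0 = 0.5. The cells are:
- a = e·p1 (drinking cases)
- b = e(1−p1) (drinking non-cases)
- c = (1−e)p0 (non-drinking cases)
- d = (1−e)(1−p0) (non-drinking non-cases)

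If a fraction f of cell a is recorded as non-drinkers, the observed OR = (a − fa)·d / [b·(c + fa)].

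**Worked case, OR 1.5 and e = 50%.** Here p1 = 0.5505 and p0 = 0.4495, so a = d = 0.2753 and b = c = 0.2248.
- f = 10%: 0.2477 × 0.2753 / (0.2248 × 0.2523) = 1.20
- f = 20%: 0.2202 × 0.2753 / (0.2248 × 0.2798) = 0.96

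**Where the observed OR reaches 1.** This happens when recorded consumption is equal in cases and non-cases. At 50% prevalence that gives f = 1 − b/a = 1 − (1−p1)/p1.

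| True OR | e | p1 | f at which observed OR = 1 |
|---|---|---|---|
| 1.5 | 30% | 0.571 | 25% |
| 1.5 | 50% | 0.551 | 18% |
| 1.5 | 70% | 0.530 | 11% |
| 2.0 | 30% | 0.620 | 39% |
| 2.0 | 50% | 0.586 | 29% |
| 2.0 | 70% | 0.551 | 19% |

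**Other parametrisation.** Fix consumption in non-cases at 50%. An OR of 1.5 then means 60% of cases consume. If 20% of those stop, 0.60 × 0.8 = 0.48 and the OR is 0.48/0.52 = 0.92.

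**Against sampling error.** With 192 cases (92.2 recorded consumers, 99.8 not) and 192 non-cases (96 and 96), the standard error of the log OR is √(1/92.2 + 1/99.8 + 1/96 + 1/96) = 0.20. The shift ln(1.5/0.92) = 0.49 is about 2.4 standard errors. A larger sample would not shrink it.

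**Stress, if analysed.** Take a true OR of 1.0, with 50% stressed and 50% prevalence, so each cell is 0.25. If 10% of symptomatic unstressed students become stressed, the observed OR is 0.275/0.225 = 1.22. At 20% it is 0.30/0.20 = 1.50.

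**What the sensitivity analysis can recover.** In the worked case with f = 20%, excluding those who stopped gives (1−f) × OR = 0.8 × 1.5 = 1.20. Reclassifying them as drinkers returns 1.50, provided their answers are accurate. Exclusion alone is therefore a partial correction.

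**The case against.** Much of the case against a strong version of this point stands.

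- **The form is not shown.** A reader might infer that nothing collected bears on timing or habit change. The document does not establish that. The exposure examples are an open list and no item wording is given, so one can say only that the protocol describes no such item.
- **The size is assumed.** A reader might infer that drink odds ratios will be reversed. No document figure supports any stopping rate. The calculation has cases stopping completely and non-cases not changing at all, whereas a partial cut need not alter a yes/no answer. The result also depends on set-up: a true OR of 2.0 with 30% stopping gives 0.98 with 50% of all students drinking, but 0.467/0.533 = 0.875 with 50% of non-cases drinking. The Protocol's background cites a Lebanese student survey that found coffee or tea correlated with more symptoms. That argues against assuming reversal, though it does not exclude attenuation.
- **Stress may not be modelled.** It is not among the named regressors, so the protocol does not clearly plan an analysis that would label it a cause.
- **The limitation is generic.** Any cross-sectional study has it, and the Rational section already speaks of association. This makes the wording easy to align. It does not remove the causal verb from the objective and the research question.

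**Conclusion.** The point holds as a mismatch between wording and design, together with a gap in what the protocol describes collecting. The objective and research question ask for factors that raise prevalence. A single questionnaire with a dated outcome and undated exposures supports association only. Habit change could bias drink odds ratios toward or below 1 by an unknown amount. The thresholds of 11% to 25% (true OR 1.5) and 19% to 39% (true OR 2.0) show that moderate stopping would be enough. They rest on the protocol's 50% prevalence, on assumed consumption of 30% to 70%, and on complete stopping confined to cases.

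The document does not support reading this as a failed design or a predicted reversal. The prevalence objective is unaffected. An SAP could restrict interpretation, but it could not recover an item that was never asked, so the questionnaire is the place to act. This is a cheap improvement worth making before launch.

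**What to change.** 1. Reword objective 3 and the research question to ask for factors associated with overactive bladder, matching the Rational section, and limit the conclusions to association.
2. Before or at the planned 40-student pilot, give the drink items one defined reference period for all respondents. Cover coffee and tea as well as soft drinks, since both enter the regression.
3. Add one item, put to everyone, asking whether they have reduced coffee, tea or soft drinks because of urinary symptoms.
4. Keep reported intake as the main analysis. Add a sensitivity analysis that excludes or reclassifies those who reduced, preferably reporting both.

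Recalled earlier intake should not replace reported intake in the main analysis for the reducers alone. They would be mostly cases, so exposure would be measured differently in cases and non-cases. A student who cut down and improved to a score below 18 would also enter as a high-intake non-case.

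The cost is a slightly longer form, some recall error and a few words of protocol text. The added items do not settle direction for stress, where the rewording is the only remedy.

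### The sample size of 384 is credited with 80% power, but power does not enter the calculation and is tied to no comparison

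*Protocol*

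**What the plan says.** Under A. Technical design, Sampling, the Protocol starts from the student population ("We calculated the sample size based on the total medical students in Egypt, which is 121,320") and an expected prevalence of 50%. It then lists "an 80% power, 95% confidence interval (95% CI), and a 5% error margin, we calculated the sample size via Epi Info" and reports the result: "to become 384, and adding a 10% non-response rate, the final sample size will be 422 students".

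The 80% is presented there as one of the inputs. Three other places could in principle give it a meaning:

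- **Hypothesis:** "We hypothesize that overactive bladder is a common condition in Egyptian medical students". No threshold is given for what counts as common.
- **Statistical analysis, group comparisons:** "We will assess the difference between the baseline data, such as sex, academic year, on the overactive bladder prevalence". No difference or group sizes are given.
- **Statistical analysis, logistic regression:** "the relation between risk factors, such as history of UTI, soft drinks, coffee, or tea, on the presence of overactive bladder symptoms". No odds ratio or exposure frequency is given.

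**The concern.** Power is the probability that a particular test detects a particular alternative. A calculation that fixes the width of a confidence interval for one proportion has neither a test nor an alternative, so an 80% listed among its inputs has no role. The sentence therefore describes a calculation that cannot have been done as stated.

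The design is called analytical, and two of the three listed objectives (effect on quality of life, risk factors) depend on comparisons and regressions. Someone who reads that the study has 80% power could reasonably apply it to those objectives, and could then take a non-significant risk factor as evidence of no association. Nothing in the calculation supports that.

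**Working it through.** **Inputs from the Protocol (Sampling):** N = 121,320; p = 0.50; margin d = 0.05; 95% confidence, so z = 1.96; 10% added for non-response; power 80% (stated). The background section cites student prevalences from two neighbouring countries: "They reported a prevalence of 44.5% and 54.1%, respectively".

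**Step 1. Reproduce 384 without power.**

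- n = z² p(1−p) / d² = 1.96² × 0.25 / 0.0025 = 384.16.
- With finite population correction: 384.16 / (1 + 383.16/121,320) = 382.95.
- Non-response: 384 × 1.10 = 422.4, stated as 422.

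The stated figures are reproduced, and the 80% was not used.

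**Step 2. What 384 delivers.** The 95% CI half-width is 1.96 × √(p(1−p)/384).

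| Prevalence | Half-width (points) |
|---|---|
| 50% (planning value) | 5.00 |
| 44.5% (cited) | 4.97 |
| 54.1% (cited) | 4.98 |

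**Step 3. Could 80% power have been used and still give 384?** The nearest reading treats the 5-point margin as a difference to be detected. This is an assumption, since the Protocol plans no such test. For a one-sample normal test of 50% against 55%:

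n = [(z_α × 0.5 + 0.8416 × √(0.55 × 0.45)) / 0.05]²

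| Assumed test | n for 80% power | Power at n = 384 |
|---|---|---|
| Two-sided 5% (z_α = 1.96) | 782.5, so 783 | about 50% |
| One-sided 5% (z_α = 1.645) | 616.2, so 617 | about 62% |

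Neither version gives 384. The 50% in the two-sided row is no coincidence: at 50% power the power term z is 0 and the formula reduces to the precision formula of Step 1.

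**Step 4. What 384 supports for a two-group comparison (illustration).** Assumptions: unadjusted two-proportion test, pooled variance under the null, two-sided 5%, overall prevalence 50%, groups of 192 and 192.

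- At a difference of 14.3 points (57.1% vs 42.9%), the standard error is √(0.25 × 2/192) = 0.0510 under the null and √(2 × 0.571 × 0.429/192) = 0.0505 under the alternative.
- Power = Φ((0.143 − 1.96 × 0.0510)/0.0505) ≈ 0.80.
- For a 5-point difference, the same test has about 16% power.
- With unequal groups the detectable difference grows: about 15.5 points at an assumed 70:30 split and about 23 points at 90:10.

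**The case against.** The strongest reply is that this is a surplus phrase. The number is right, no analysis depends on the 80%, and the Sampling paragraph never says that the power applies to sex, academic year or any risk factor, so the misreading is inferred. Effect sizes for secondary comparisons may also sit in a statistical analysis plan that is not available here. Finally, the 50% versus 55% test is not one the Protocol plans, so its figures measure no defect.

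Some of this stands. The prevalence estimate is unaffected, and the one-sample figures serve only to rule out a charitable reading. The absence of a power calculation for secondary comparisons is not the complaint either. What remains is that the Protocol itself makes a power claim that is wrong as written, and no later document can turn power into an input of a formula that does not contain it.

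Two side points are fair and bear on the replacement wording. The half-width formula assumes simple random sampling, whereas the Protocol uses convenience sampling through social media. And 422 with 10% non-response leaves 422 × 0.9 ≈ 380 respondents, not 384. The half-width is then 1.96 × √(0.25/380) = 5.03 points, a negligible change.

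**Conclusion.** The concern holds. The 384 is a precision-based size: it follows from 50% prevalence, a 5-point margin and 95% confidence, and it is the same for any stated power. The Protocol links the 80% to no null value, effect size or comparison, so the study is credited with a property that its calculation does not have.

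The first objective is not harmed. The consequence lies with the associational objectives, where only differences of roughly 14 points or more would be detected with 80% power, under the assumed equal split, 50% overall prevalence and an unadjusted test. The Protocol gives no group sizes, so that figure is indicative only. The statement should be corrected before it is carried into a report.

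**What to change.** Remove the reference to 80% power from the Sampling paragraph and state what the number delivers, for example:

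> 384 respondents give a 95% CI half-width of 5 percentage points at an expected prevalence of 50%, calculated as for a simple random sample.

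If a power statement is wanted, keep it separate and tie it to one named comparison with its assumptions. Prevalence by sex is one possibility:

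> Unadjusted two-proportion comparison, two-sided 5%, overall prevalence 50%, assuming half of the 384 respondents are women: 80% power for a difference of about 14 points (about 57% vs 43%).

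The comparison and the expected split are for the investigators to choose, and the detectable difference must be recalculated if either changes.

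The cost is wording only: 384, 422 and the planned analyses are unchanged. The study gives up a general claim of 80% power for its associational objectives unless it names a comparison.

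### The allowance for a 10% loss is added to 384 rather than divided out, so 422 students leave about 380, slightly under the protocol's own target

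*Protocol*

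**What the plan says.** The sample size is set out in the Protocol under Methodology, A. Technical design, in the Sampling paragraph. The inputs are a population of "total medical students in Egypt, which is 121,320", an expected prevalence of 50%, and a "95% confidence interval (95% CI), and a 5% error margin". These give a base size of 384. The allowance for losses follows in one step: "adding a 10% non-response rate, the final sample size will be 422 students". The inflation formula is not written out.

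The same section lists three exclusions: incomplete questionnaires, "Wrong data in the questionnaire", and refusal to take part. Sampling is by convenience, and the Operational design has the questionnaire circulated on social media platforms. The protocol does not say which of these losses the 10% is meant to cover, or whether 422 counts students approached, questionnaires received or questionnaires analysed.

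**The concern.** An allowance for losses should leave the required number after the losses have occurred. If a fraction L of the starting number is lost, the starting number must be the required number divided by (1 − L). Adding L times the required number gives slightly too few, because the loss then acts on the larger, inflated figure. The stated 422 looks like the result of adding.

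What is at stake is whether the stated size delivers the stated margin. Prevalence is the first listed objective, and the 5-point margin is the precision target from which 384 was derived. If the three figures (384, 10% and 422) do not fit together, the protocol falls slightly short of its own target under its own assumptions.

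**Working it through.** **Inputs, all from the Sampling paragraph of the Protocol:** N = 121,320; p = 0.50; 95% confidence, so z = 1.96; margin d = 0.05; loss L = 0.10; base size 384; final size 422. The 80% power also listed there does not enter a precision calculation for a single proportion.

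**1. Reproduce the base size.**
- Without finite-population correction: n₀ = z² p(1 − p)/d² = 1.96² × 0.25/0.0025 = 384.1, which gives the stated 384.
- With correction for N = 121,320: n₀/(1 + (n₀ − 1)/N) = 382.9, so 383. The difference is immaterial.

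**2. Reproduce the final size.**
- 384 × 1.10 = 422.4, which gives the stated 422. The allowance was therefore added to the base.

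**3. Apply the stated loss to 422.**
- 422 × (1 − 0.10) = 379.8, about 380. That is 4 below 384, and also below the finite-population figure of 383.

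**4. Size that survives a 10% loss.**
- 384/0.90 = 426.7, so 427. Check: 427 × 0.90 = 384.3. This is 5 students more than 422 (5/422 = 1.2%).
- From a base of 383 the result is 383/0.90 = 425.6, so 426.

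**5. Loss that 422 can absorb.**
- 1 − 384/422 = 0.090, that is 9.0% or 38 losses.

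**6. Effect on the margin at p = 0.50, half-width = 1.96 × √(0.25/n).**

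| n | Half-width | With finite-population correction |
|---|---|---|
| 384 | 5.00 points | 4.99 points |
| 380 | 5.03 points | 5.02 points |

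**7. Sensitivity to p.** The Protocol's background gives 44.5% and 54.1% for the two student surveys cited in support of the 50%. With n = 380:
- 1.96 × √(0.445 × 0.555/380) = 5.00 points
- 1.96 × √(0.541 × 0.459/380) = 5.01 points

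**The case against.** **The consequence vanishes at the precision quoted.** The margin is given in whole per cent, and 5.03 points is still 5%. The assumed 50% is also the least favourable prevalence; at the two cited prevalences, 380 respondents give 5.00 and 5.01 points. In a convenience sample, a change of 0.03 points in a nominal margin alters no analysis and no interpretation. All of this stands. It limits the point to a correction of a stated figure, but it does not make the three figures agree.

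**The shortfall depends on what 422 counts.** With an open link, students who do not respond never enter a count, so 422 might mean questionnaires received, or even completed questionnaires. If it means received, 384 remain unless more than 38 are excluded. If it means completed and analysable, the target is exceeded. This also stands in part: the protocol does not define 422, and the shortfall exists only if it is a number before losses. That is nevertheless the natural reading, because a non-response allowance has no purpose if 422 is already net of losses.

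**The wording describes what was done.** The text speaks of adding 10%, and 422 is 384 plus 10%, so the figure reproduces. That is true. The weakness lies in the method of inflation, not in a slip of multiplication.

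**A stronger reading that the protocol does not support.** A reader might infer from the exclusion of incomplete and wrong questionnaires that no allowance has been made for them, and might then apply a second loss on top of the 10%. The protocol lists these exclusions alongside refusal, gives a single 10%, and does not say which losses it covers. It may be meant to cover all of them. No separate rate of exclusion is given, so a larger shortfall or a wider margin than the one shown above would rest on an invented figure.

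**Conclusion.** The point holds as a minor correction. Taken as the number before losses, 422 leaves about 380 at the stated 10% loss, against the required 384. The margin at 50% prevalence becomes 5.03 rather than 5.00 points. The figure that matches the stated inputs is 427.

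This rests on two assumptions: that 422 counts students or questionnaires before losses, and that the loss is the full 10%. At a loss of 9.0% or less there is no shortfall. A reader might take the point as evidence that the prevalence estimate will be imprecise; about 4 respondents and 0.03 points do not support that.

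**What to change.** In the Sampling paragraph, make one of these changes:

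- Restate the final size as 427 (384/0.90).
- Keep 422 and say that at a 10% loss it yields about 380 respondents and a margin of 5.03 points at 50% prevalence.
- State the target as 384 eligible, analysable questionnaires after the protocol's exclusions, and keep the link open until that number is reached.

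The third suits an open link best. It settles what the number counts and does not depend on a non-response rate, for which the protocol describes no list of invited students as a denominator.

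The cost is one edited sentence. The first option asks for 5 more students; the third may keep the link open a little longer. The instrument and the analysis do not change.

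### The 5% margin behind the sample size is a simple-random-sampling figure for all Egyptian medical students, but recruitment is by convenience, so it is not the precision of a national prevalence estimate

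*Protocol*

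**What the plan says.** The first item under Objective in the protocol is "To assess the prevalence of overactive bladder among Egyptian medical students", with no qualification of the target group.

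Under A. Technical design, the Sampling item ties the number to that national group: "We calculated the sample size based on the total medical students in Egypt, which is 121,320". The inputs are an expected prevalence of 50%, with "95% confidence interval (95% CI), and a 5% error margin", which give 384. The final step is "adding a 10% non-response rate, the final sample size will be 422 students".

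The next item, Sampling techniques, reads: "The convenient sampling will be applied in this study". Under B. Operational design, Study field adds that "an online questionnaire will be shared through social media platforms such as WhatsApp, Facebook, or Telegram".

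The protocol mentions no sampling frame, quota, weighting or design effect, and nothing that limits the national target.

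**The concern.** A margin of error computed from a sample-size formula holds for a sample in which every member of the population has a known chance of selection. In its simplest form, that chance is equal for all. Here the chance of entering the sample depends on who sees a link and decides to answer, and that decision may be related to having bladder symptoms. The protocol places the national population, the 5% margin and convenience sampling in consecutive items and does not say that the margin fails to carry over.

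The first of the three objectives is at stake. If the study reaches 384 or 422 answers, a reader of the Sampling section would naturally take the prevalence as a national figure good to about 5 points. The design does not deliver that. Collecting more answers would not help, because self-selection does not shrink as the sample grows.

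**Working it through.** **Inputs, all from the Sampling item of the protocol.** N = 121,320; p = 0.50; 95% confidence (z = 1.96); d = 0.05, read as absolute; 10% addition. The stated 80% power does not enter a precision formula for one proportion.

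**1. Reproduce the plan's figure.**
- Simple random sample, design effect 1: n0 = z² p(1 − p)/d² = 3.8416 × 0.25/0.0025 = 384.16.
- With finite-population correction: n0/(1 + (n0 − 1)/N) = 384.16/(1 + 383.16/121,320) = 382.95, that is 383.
- With the addition: 384 × 1.10 = 422.4, stated as 422.

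The arithmetic is sound. The stated 384 matches the simple-random-sample formula and leaves no allowance for any other design.

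**2. What the 5% covers.** The half-width is 1.96 × √(0.25/n).
- n = 384: 0.0500, or 5.0 points.
- n = 422: 0.0477, or 4.8 points.

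Both are random-sampling error only. Raising 384 to 422 protects the count of answers. It does nothing about differences between those who answer and those who do not.

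**3. How much selection would use up the margin.** The protocol gives no participation figures, so the ratio k below is an assumption. Let symptomatic students be k times as likely to answer as asymptomatic ones. The expected observed prevalence is then

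p·k/(p·k + 1 − p).

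The sample size does not appear in this expression, so the shift is the same at any n. The ratio that produces a shift of d is

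k = [(p + d)/(1 − p − d)] / [p/(1 − p)].

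At the planning value p = 0.50:
- Shift of +5 points: k = 0.55/0.45 = 1.22.
- Shift of −5 points: k = 0.45/0.55 = 0.82.
- Milder ratio, k = 1.1: 0.55/1.05 = 0.524, a shift of +2.4 points.
- Milder ratio, k = 0.91: 0.455/0.955 = 0.476, a shift of −2.4 points.

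**4. Sensitivity to the planning value.** The protocol's background cites 44.5% and 54.1% in medical students in Jordan and Palestine. With k = 1.22 these become 49.5% and 59.0%, shifts of 4.9 to 5.0 points. The result hardly depends on where in that range the true value lies.

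**The case against.** The strongest reply is that the protocol promises less than a critic might read into it. The 5% is an input to the sample-size calculation. No sentence says that the prevalence will be reported with a 5-point interval, and the Statistical analysis section plans only counts and percentages for categorical data. A reader might infer that the protocol commits to a national estimate with that precision, but the text does not go that far. What stands is narrower and does not need that commitment: the number is justified by a precision that the sampling method cannot give, for a national target left unqualified.

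Convenience sampling is also openly declared, and nowhere is random sampling claimed. That is true. The fault is not the use of convenience sampling but the margin attached to it.

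How results are described and tabulated may be left to a statistical analysis plan, which is not at hand, or to the report. That is fair for the make-up tables. The population, the margin and the sampling method, however, are all fixed in this protocol, so the qualification belongs there.

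Finally, a reader might infer that university and region are not collected, because the sociodemographic items listed under Data collection method are age, sex and academic year. The documents do not support this. The questionnaire is not shown and the list is evidently incomplete: history of UTI, coffee and tea appear in the planned analysis but not in the list. No defect is claimed on that point.

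**Conclusion.** The point holds as a mismatch between the stated precision and the sampling method. The 384 is correct for a simple random sample. The design is not one, so the 5% is random-sampling error only and should not stand as the precision of a national prevalence. This conclusion needs no assumed participation ratio.

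The size of the effect is another matter. The 1.22 and 0.82 show only that a modest imbalance in participation would equal the whole margin at 50% prevalence. They are assumptions, not estimates. A reader might conclude that the prevalence will be overstated because symptomatic students are keener to answer. The documents give no basis for either direction or size, and that conclusion should not be drawn.

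The correction is worth making before launch. It changes what the study may conclude on its first objective, but it does not make the survey unworkable.

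**What to change.** Keep the online survey and the target of 422.

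1. In the Sampling section, state that 384 gives a 5% margin only under simple random sampling, and that under convenience sampling this figure excludes selection error.
2. Word the prevalence objective and the conclusion as prevalence among respondents, or explicitly qualify the national claim.
3. If university and region are not already on the form, add them at the pilot stage, for which the protocol already allows changes: "We will perform it on 40 students, and any changes in the questionnaire will be made". Report the make-up of the sample by university, region, sex and academic year. These items are hard to recover after collection.

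The cost is one or two sentences, at most one or two extra questions, and a more modest headline claim. The gain is limited too: selection is disclosed and the sample's make-up becomes partly checkable, but the selection itself is not removed.
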